### 4.2 Inclusion Criteria

Subjects who have successfully completed Study RB-US-13-0003 EOS assessments, which will serve as screening for this study. In addition, **only** the following criteria must be met to be enrolled in this study:

1. Provide written consent to participate in this study.
2. Completed the End of Study Visit for the RB-US-13-0003 study.
3. Be considered eligible in the medical judgment of the Investigator.
4. Females: Women of childbearing potential (defined as all women who are not surgically sterile or postmenopausal for at least 1 year prior to ICF) must have a negative pregnancy test prior to enrollment and must agree to use a medically acceptable means of contraception from screening through at least 6 months after the last dose of investigational medicinal product (IMP).

Males: Subjects with female partners of child-bearing potential must agree to use medically acceptable contraception after signing the ICF through at least 6 months after the last dose of IMP. Male subjects must also agree not to donate sperm during the study and for 6 months after receiving the last dose of IMP.

The following methods of contraception are considered to be medically acceptable: established use (for a period of at least 1 month) of oral, injected or implanted hormonal contraception; placement of an intrauterine device or intrauterine system; use of a double-barrier method of contraception (condom or occlusive cap with use of a spermicide) or male sterilization.

5. Subjects must agree not to take any buprenorphine products other than those administered during the current study throughout participation in the study.
6. Subjects must be willing to adhere to study procedures.

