### 6.5.4 Laboratory Results Review

The Investigator will review the results and comment on the laboratory results sheet for all abnormal values, identifying those that are abnormal but not clinically significant as well as those that are significantly abnormal. The Investigator will sign and date the laboratory results sheet to indicate that the review has taken place.

**Clinical Laboratory Changes:** It is the Investigator's responsibility to review the results of all laboratory tests as they become available. This review will be documented by the Investigator on the laboratory report. For each abnormal laboratory test result, the Investigator needs to ascertain if this is a clinically significant abnormal change from baseline for that individual subject.

Any liver abnormality  $> 3 \times \text{ULN}$  should be carefully assessed by the Investigator to determine whether it should be considered an AE. Guidance for the procedures to follow for elevated liver function tests are provided in [Appendix 8](#).

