### 6.9.9 Clinical Laboratory Adverse Events

Changes in laboratory values or vital signs, or other safety parameters (e.g., neurological and clinical symptom assessments) as noted in the protocol are a subset of AEs and are reportable only if considered to be clinically significant by the Investigator or medically qualified Sub-investigator except that:

- Baseline assessments are differentiated from AE/symptoms that are incurred post informed consent. These baseline lab assessments, if determined to be clinically significant abnormal values, reflect the status of the subject prior to study participation. These clinically significant pre-dose abnormal assessments without clinical symptoms will not be reported as AEs.

It is noted that any liver abnormality  $> 3 \times$  ULN should be carefully assessed by the Investigator to determine whether it should be considered an AE. Guidance for the procedures to follow for elevated liver function tests are provided in [Appendix 8](#).

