12.2 CLINICAL LABORATORY PARAMETERS

Laboratory data will be reported using International System (SI) units (and using original units for some parameters if necessary) as collected by the central laboratory. Unless otherwise specified, all continuous laboratory data will be summarized using descriptive statistics (n, mean, SD, median, min and max) for each scheduled study assessment as well as change from baseline and percentage change from baseline [if applicable] by parameter class (hematology, chemistry, and urinalysis). All laboratory assessments include a baseline summary as defined in Section 20.2 unless otherwise indicated. Hematology chemistry and urinalysis data will be summarized by displaying shifts from baseline value to EOS/ET visit. All laboratory assessments will be listed by panel with the corresponding normal ranges for each parameter. Screening laboratory tests will also be listed.

The peak total bilirubin [x ULN] vs. peak aspartate aminotransferase (or peak alanine aminotransferase) [x ULN] on a log/log scale during the Treatment Period will be plotted in the Safety Analysis Set. And the box plot to access clinical liver safety data by maximum change from baseline during the Treatment Period will be plotted for lab tests ALT, AST and total bilirubin.

Summary of potential hepatotoxicity for serum chemistry by type of criterion (shown in Table 5) and by analysis visit and at any time post baseline will be tabulated for the Safety Analysis Set. For “Any time post baseline”, a subject will be classified to their highest/worst applicable toxicity grade per criterion, among the post baseline visits including unscheduled visits, and be counted only once in the category corresponding to the worst grade. For subjects who met the criteria for potential hepatotoxicity (any time post baseline), their test results for ALT, AST, TBIL, ALP during study (i.e., at all scheduled and unscheduled visit) will be provided in a listing.

Table 5: Criteria for Potential Hepatotoxicity Laboratory Value

Criteria
ALT > 3 x ULN to < 5 x ULN
ALT \geq 5 x ULN to < 8 x ULN
ALT \geq 8 x ULN
AST > 3 x ULN to < 5 x ULN
AST \geq 5 x ULN to < 8 x ULN
AST \geq 8 x ULN
ALT & AST > 3 x ULN to < 5 x ULN
ALT & AST \geq 5 x ULN to < 8 x ULN
ALT & AST \geq 8 x ULN
TBIL > 2 x ULN to < 5 x ULN
TBIL \geq 5 x ULN
HYs Law: (all must be met to meet Potential Hy's law)
ALT or AST > 3 x ULN
TBIL > 2 x ULN
ULN < Alkaline phosphatase (ALP) < 2xULN

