20.2 ANALYSIS VISITS AND OTHER DEFINITIONS

All data will be presented in listings (including unscheduled visits), however only per-protocol visits will be summarized in tables and figures. Unscheduled and scheduled assessments will be utilized in the summaries for “at any time”.

For lab values, body weight, BMI, waist circumference, hip circumference and waist-to-hip ratio, Early Termination and End-of-study results will be reported with the EOS/ET visit.

For all other assessments, occurring at the ET visit, will be mapped to the next per-protocol visit (or time point), that has not already been completed by the subject. A ET visit must not be mapped to a visit that a subject has already completed.

The closest assessment value on or before Treatment Start Date/Time will be assigned as Baseline value and then be labeled as 'Baseline' in visit window, and for assessment prior to Treatment Start Date/Time, if exists, will be labeled as 'EOS 0003' or 'Screening' per its collecting time and per SOE definition.

For subjects who have one visit-based assessment in the Safety Follow-up (SFU) period, the period of the visit will be labeled as 'Safety Follow-Up Week 29'.

Other Definitions:

Subgroups

Sex

- Male
- Female

Age Categories

- ≥ 18 to < 30
- ≥ 30 to < 45
- ≥ 45 to < 60
- ≥ 60
- ≥ 65

Race

- White
- Non-White

Baseline BMI Categories

- Under weight: 0 to $< 18.5 \text{ kg/m}^2$
- Normal: $\geq 18.5 \text{ kg/m}^2$ and $< 25 \text{ kg/m}^2$
- Over weight: $\geq 25 \text{ kg/m}^2$ and $< 30 \text{ kg/m}^2$
- Obese: $\geq 30 \text{ kg/m}^2$

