20.9 CHARACTER VALUES OF CLINICAL LABORATORY PARAMETERS AND OTHER LABORATORY IMPUTATION RULES

- If a reported value of a clinical laboratory parameter cannot be used in a statistical summary table due, for example, to the fact that a character string is reported for a parameter of the numerical type, a coded value needs to be appropriately determined and used in the statistical analyses. Value of X+0.0001 will be used to impute ">X" character value and X-0.0001 will be used to impute "<X". That is, if X equal to 60, 60.0001 will be used to impute character value of ">60" and 59.999 will be used to impute "<60". However, the actual values as reported in the database may be presented in data listings.
- Due to the fact that screening lab records were rolled-over from RB-US-13-0003, whose LDH, total bilirubin and AST records have lower limits and HDL-C records have upper limit as opposed to at visits after first injection only having one-sided upper limits for parameters LDH, total bilirubin and AST and one-sided lower limit for HDL-C, lab classification values (i.e., Low, normal and high) for parameters LDH, total bilirubin and AST and HDL-C at screening and from RB-US-13-0003 should be imputed so that shift tables can be tabulated. The imputation rules are as follows:
 - For screening records (ie, rolled-over from RB-US-13-0003) of parameters LDH, total bilirubin and AST, lower limits will be imputed as 0. The lab character values of "Low" and "Normal" will be collapsed to be "Normal".
 - For screening records (ie, rolled-over from RB-US-13-0003) of HDL-C, upper limit will be imputed as blank. The lab character values of "Normal" and "High" will be collapsed to be "Normal".
- GGT assessments at Screening have categories of normal and high but have three categories of low, normal and high post-baseline. Then for GGT post-baseline assessments, low and normal will be collapsed to normal.

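### The potential-hepatotoxicity table (SAP 12.2, Table 14.3.5.4) takes no account of each subject's baseline, and no planned table counts new or worsened crossings of the liver-test thresholds

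*SAP*

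**What the plan says.** SAP 12.2 plans a summary of potential hepatotoxicity by the Table 5 criteria (output Table 14.3.5.4), "by analysis visit and at any time post baseline will be tabulated for the Safety Analysis Set". The criteria are fixed multiples of ULN. For ALT the lowest band is "ALT > 3 x ULN to < 5 x ULN", with further bands starting at 5x and 8x. AST has the same bands, and total bilirubin (TBIL) has bands starting above 2x and at 5x. For the any-time row, "a subject will be classified to their highest/worst applicable toxicity grade per criterion, among the post baseline visits including unscheduled visits". No criterion refers to the subject's own baseline.

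The SAP does define a baseline. In 20.2, "The closest assessment value on or before Treatment Start Date/Time will be assigned as Baseline value". For chemistry this is the sample from the RB-US-13-0003 end-of-study visit (Protocol Appendix 1; SAP 12.2.2).

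On entry, Protocol 4.2 says that only "the following criteria must be met to be enrolled in this study". Neither that list nor the exclusions in 4.3 contains an ALT, AST or bilirubin limit. One listed criterion is the investigator's medical judgment.

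Other planned outputs do use baseline: change and percentage change, a shift table from baseline to EOS/ET (Table 14.3.5.6), a box plot of maximum change in ALT, AST and TBIL (Figure 14.3.5.4.3), a listing of screening laboratory data (16.2.29), and a listing of liver-test results for every subject who met a criterion (16.2.33). SAP 12.2 also says in general terms that laboratory assessments include a baseline summary.

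**The concern.** In a safety extension, the obvious question for the liver laboratory data is how many subjects newly reached, or worsened to, 3x, 5x or 8x ULN during the study (2x or 5x for TBIL). Table 14.3.5.4 looks as if it answers this, but it counts anyone whose worst later value is above the line, wherever that person started. Because nothing at entry keeps out subjects who are already elevated, the count can mix carried-over with new elevations in unknown proportions.

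The protocol makes the distinction elsewhere for its own purposes. On baseline laboratory findings, 6.9.9 says: "These baseline lab assessments, if determined to be clinically significant abnormal values, reflect the status of the subject prior to study participation". On abnormal results during the study, 6.5.4 says that "the Investigator needs to ascertain if this is a clinically significant abnormal change from baseline for that individual subject". Hepatic disorders are also one of the SAP's topics of special interest (12.1.7). A summary table that drops the distinction leaves a gap in the safety report.

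**Working it through.** The plan states no rate, power or expected count for liver tests, so there is no figure to reproduce. The check applies the written rules to constructed cases and then gives an illustration with assumed rates.

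**Step 1. Apply the rules to constructed ALT values (multiples of ULN).** The shift class is High above 1x ULN and Normal otherwise.

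| Baseline → worst later value | Table 5 band | Shift class | Change |
|---|---|---|---|
| 4 → 4 (unchanged) | >3 to <5 | High → High | 0 |
| 4 → 3.2 (improved) | >3 to <5 | High → High | −0.8 |
| 0.8 → 4 (new) | >3 to <5 | Normal → High | +3.2 |
| 4 → 9 (worsened) | ≥8 | High → High | +5 |
| 0.8 → 9 (new) | ≥8 | Normal → High | +8.2 |

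The first three subjects fall in the same Table 5 band although one is unchanged, one improved and one is new.

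**Step 2. Ask whether another output supplies the missing count.**

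- *Shift table.* SAP 20.9 describes harmonising "lab classification values (i.e., Low, normal and high") so that shifts can be tabulated. It names AST and TBIL among the tests concerned, and nothing suggests other classes for ALT. These classes miss worsening from an already high baseline (4 → 9), and Normal → High does not tell 4x from 9x. The table runs to EOS/ET, and under SAP 20.2 unscheduled results enter only the any-time summaries, so an unscheduled peak that settles by EOS/ET is not seen.
- *Box plot.* It shows the size of the change, not whether a threshold was crossed.
- *Hepatic TEAE table (14.3.1.16).* A TEAE must start after the first dose or increase in severity (SAP 12.1.1), so baseline is respected. It counts what was reported as an AE, not ULN multiples.
- *Listings 16.2.29 and 16.2.33.* These allow every flagged subject to be sorted by hand, but they are not a count.

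**Step 3. Ask what a baseline row would add.** Let B be the number above a threshold at baseline, R those of them who are later below it, and W the new cases. The post-baseline count is B − R + W, so post-baseline minus baseline is W − R. If R = 0, subtraction recovers W: with B = 15 and W = 3 in 300 subjects, the rows read 15/300 = 5.0% and 18/300 = 6.0%, and the difference is 1.0%. If R > 0 it does not. With B = 15, 70% persisting (10.5) and 1% new among the other 285 (2.85), the post-baseline count is 13.35. The difference is −1.65 although 2.85 are new.

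**Step 4. Illustrate the size.** N = 300 is the planned enrolment (SAP 18.0). All other inputs are assumptions: baseline prevalence b of 1% to 10%, 70% of those still above the threshold later, new elevations at rate p = 1% or 3% among the rest, and a post-baseline value for everyone. Carried over = 300 × b × 0.7, and new = 300 × (1 − b) × p.

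| b | p | Carried over | New | Table count | Share carried over |
|---|---|---|---|---|---|
| 1% | 1% | 2.1 | 3.0 | 5.1 | 41% |
| 5% | 1% | 10.5 | 2.9 | 13.3 | 79% |
| 10% | 1% | 21.0 | 2.7 | 23.7 | 89% |
| 1% | 3% | 2.1 | 8.9 | 11.0 | 19% |
| 5% | 3% | 10.5 | 8.5 | 19.0 | 55% |
| 10% | 3% | 21.0 | 8.1 | 29.1 | 72% |

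At b = 0 the carried-over share is 0 and the table count equals the new count.

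**The case against.** The strongest reply is that the information is not lost. Chemistry is scheduled only at baseline and EOS/ET, so most flagged subjects have about two values to compare, and Listings 16.2.29 and 16.2.33 show them. That stands. A reader might infer that worsening cannot be identified at all, and the documents do not support that. What is missing is a prespecified count.

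A second reply is that Table 14.3.5.4 may well contain a baseline row, given the general baseline-summary sentence and the by-visit layout. Only table titles are given, so this can be neither confirmed nor excluded. If the row exists it helps, but it shows new minus resolved cases, not new cases.

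Third, a reader might infer that the SAP contradicts Protocol 6.5.4 and 6.9.9. It does not. Those sections govern the investigator's review of results and what is reported as an AE, not how tables are built. Protocol 9.5.1.2 asks for absolute values and change from baseline, and the SAP provides both.

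Fourth, the unconditional count is defensible in its own right. Baseline was taken after treatment with RBP-6000 in RB-US-13-0003, so an elevated baseline may itself be drug-related. This stands and is the reason to keep that count.

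Finally, the documents do not show that anyone entered above 3x ULN. Protocol Table 1 lists abnormal liver function tests among the common possibly related AEs of two earlier studies, but it gives no magnitude and concerns other subjects. The missing entry limit shows that the situation is possible, not how often it occurs.

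**Conclusion.** The point holds as a gap in the planned summary. Table 14.3.5.4 counts unchanged and improved elevations together with new ones, and no listed table gives the number of subjects who newly reached or worsened to 3x, 5x or 8x ULN (2x or 5x for TBIL). It affects only subjects already above a threshold at baseline; a rise from 1.2x to 6x ULN, for instance, is counted correctly in Table 5 and is obscured only in the shift table.

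A reader might take the illustration as an estimate of inflation. It is not one: baseline prevalence, persistence and incidence are all assumed, and the carried-over share runs from zero (nobody elevated at baseline) to 89% within the range shown. The study is single-arm and descriptive, so no test or decision rule is affected. It is a worthwhile, inexpensive improvement to the main liver laboratory table of a safety study.

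**What to change.** In SAP 12.2 and the output list:

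- Keep the unconditional any-time count as it is.
- Beside it, add a cross-tabulation for ALT, AST and TBIL of baseline category against worst post-baseline category, including unscheduled visits. The categories are the Table 5 bands plus one for values below the lowest threshold: ≤3x, >3 to <5x, ≥5 to <8x and ≥8x ULN for ALT and AST; ≤2x, >2 to <5x and ≥5x ULN for TBIL.
- Scale each value to the ULN that came with its own sample, since SAP 20.9 shows that the form of the reference limits differs between the rolled-over screening records and later visits.
- For each test, report the number of subjects who worsened by at least one category.
- State whether the by-visit part of Table 14.3.5.4 includes a baseline row.

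The cost is a few lines of SAP text and one table shell. All values are already collected. The downside is one more table, most of whose cells will be sparse.

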14.3.5 Laboratory Data Tables

Table 14.3.5.1 Summary of Laboratory Data by Visit: Hematology - Safety Analysis Set

Table 14.3.5.2 Summary of Laboratory Data by Visit: Serum Chemistry - Safety Analysis Set

Table 14.3.5.3 Summary of Laboratory Data by Visit: Urinalysis - Safety Analysis Set

Table 14.3.5.4 Summary of Potential Hepatotoxicity by Visit: Serum Chemistry - Safety Analysis Set

Figure 14.3.5.4.1 Evaluation of Drug-Induced Serious Hepatotoxicity: Plot of Peak Total Bilirubin [x ULN] vs. Peak Aspartate Aminotransferase [x ULN] on a log/log scale During the Treatment Period – Safety Analysis Set

Figure 14.3.5.4.2 Evaluation of Drug-Induced Serious Hepatotoxicity: Plot of Peak Total Bilirubin [x ULN] vs. Peak Alanine Aminotransferase [x ULN] on a log/log scale During the Treatment Period – Safety Analysis Set

Figure 14.3.5.4.3 Evaluation of Drug-Induced Serious Hepatotoxicity: Box Plot to Assess Clinical Liver Safety Data by maximum Change from Baseline at Any Time During the Treatment Period– Safety Analysis Set

Table 14.3.5.5 Summary of Observed Laboratory Data: Shift from Baseline: Hematology – Safety Analysis Set

Table 14.3.5.6 Summary of Observed Laboratory Data: Shift from Baseline: Serum Chemistry – Safety Analysis Set

Table 14.3.5.7 Summary of Observed Laboratory Data: Shift from Baseline: Urinalysis – Safety Analysis Set

Table 14.3.5.8 Summary of Vital Signs by Visit – Observed Value and Change from Baseline – Safety Analysis Set

Table 14.3.5.9 Body Weight, BMI, Waist Circumference, Hip Circumference and Waist-to-Hip Ratio – Observed Value – Safety Analysis Set

Listings

Listing 16.2.1 Subject Analysis Sets, Disposition, Completion of Study/Discontinuation from Study – All Screened Subjects

Listing 16.2.2 Inclusion/Exclusion Criteria

Listing 16.2.3 Inclusion/Exclusion Criteria Not Met – Screen Failure subjects

Listing 16.2.4 Important Protocol Deviations – Safety Analysis Set

Listing 16.2.5 Demographic and Baseline Characteristics – All Screened Subjects

Listing 16.2.6 Medical/Surgical History – Safety Analysis Set

Listing 16.2.7 Substance Use History – Safety Analysis Set

Listing 16.2.8 Study Drug Injection and Dosing – Safety Analysis Set

Listing 16.2.9 Dose Adjustments – Safety Analysis Set

Listing 16.2.10 Prior Medications – Safety Analysis Set

Listing 16.2.11.1 Concomitant Medications During RBP-6000 Dosing – Safety Analysis Set

Listing 16.2.11.2 Concomitant Medications Post RBP-6000 Dosing – Safety Analysis Set

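### Read literally, the joint ALT & AST rows of SAP Table 5 omit subjects with both enzymes above 3 times ULN but in different bands (minor)

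*SAP*

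**What the plan says.** SAP Section 12.2 plans a table of potential hepatotoxicity "by type of criterion (shown in Table 5) and by analysis visit and at any time post baseline". Appendix 3 lists it as "Table 14.3.5.4 Summary of Potential Hepatotoxicity by Visit: Serum Chemistry - Safety Analysis Set".

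Table 5 uses the same three bands for ALT alone, for AST alone, and for the two together. The first joint row is "ALT & AST > 3 x ULN to < 5 x ULN". The second runs from 5 to below 8 times ULN, and the third is 8 times ULN or more. The first two joint rows have an upper limit. No row covers both enzymes above 3 times ULN without one.

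For the any-time column, "a subject will be classified to their highest/worst applicable toxicity grade per criterion, among the post baseline visits including unscheduled visits", and the subject is counted one time, at the worst grade. For anyone who meets a criterion at any time after baseline, "their test results for ALT, AST, TBIL, ALP during study (i.e., at all scheduled and unscheduled visit) will be provided in a listing".

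**The concern.** Bands with upper limits work for one enzyme, because each value above 3 times ULN lies in exactly one band. Applied to two enzymes at once, they cover only the pairs that happen to share a band. The joint rows then stop being ordered by severity: raising one enzyme while the other stays put can move a subject out of the joint rows altogether.

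At stake is how Table 14.3.5.4 reads. The joint rows are the only rows of Table 5 that show how many subjects had both enzymes raised. The any-time ALT and AST rows cannot be combined to recover that number, because they are separate margins and each may come from a different visit.

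**Working it through.** The plan gives no count or percentage here, so there is no figure to reproduce. The check has three parts.

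**1. Apply the rows literally.** Inputs: the three joint rows of Table 5, with both enzymes required to satisfy a row's limits. Test values, one per band: 4, 6 and 10 times ULN.

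| ALT | AST | Joint row met | Lower multiple | Row if graded by the lower |
|---|---|---|---|---|
| 4 | 4 | >3 to <5 | 4 | >3 to <5 |
| 4 | 6 | none | 4 | >3 to <5 |
| 4 | 10 | none | 4 | >3 to <5 |
| 6 | 4 | none | 4 | >3 to <5 |
| 6 | 6 | ≥5 to <8 | 6 | ≥5 to <8 |
| 6 | 10 | none | 6 | ≥5 to <8 |
| 10 | 4 | none | 4 | >3 to <5 |
| 10 | 6 | none | 6 | ≥5 to <8 |
| 10 | 10 | ≥8 | 10 | ≥8 |

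Three of the nine pairs meet a joint row and six meet none. In all six, the subject still meets one ALT-only row and one AST-only row.

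**2. Look for a rule that closes the gap.** The worst-grade rule chooses among grades that apply, so it cannot place a sample that meets no row. It can also understate: with ALT 4 and AST 4 at one visit and ALT 10 and AST 6 at another, the only joint row met is >3 to <5, so the any-time entry reflects the milder visit. SAP Sections 20.2, 20.4 and 20.9 deal with visits, repeat assessments and laboratory values. None addresses enzymes in different bands.

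**3. Size, on assumed inputs.** The documents give no ALT or AST distribution. Assume that ln(ALT/ULN) and ln(AST/ULN) are bivariate normal with common median *m*, log SD *s* and correlation *r*, with one post-baseline sample per subject (Protocol Section 9.5.1.2 schedules chemistry at screening and EOS). Then:

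- P_both = P(both > 3)
- P_same = sum over the three bands of P(both in that band)
- Discordant share = 1 − P_same / P_both
- Discordant subjects per 300 = 300 × P_both × share

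| m | s | r | P_both | Share | Both >3 per 300 | Discordant per 300 |
|---|---|---|---|---|---|---|
| 0.6 | 0.6 | 0.5 | 0.0003 | 20% | 0.1 | 0.02 |
| 0.6 | 0.6 | 0.9 | 0.0018 | 13% | 0.5 | 0.07 |
| 0.6 | 0.8 | 0.7 | 0.0071 | 40% | 2.1 | 0.8 |
| 0.6 | 1.0 | 0.5 | 0.0135 | 54% | 4.0 | 2.2 |
| 0.6 | 1.0 | 0.9 | 0.0345 | 41% | 10.4 | 4.2 |
| 0.7 | 0.8 | 0.7 | 0.0123 | 41% | 3.7 | 1.5 |
| 0.7 | 1.0 | 0.5 | 0.0207 | 55% | 6.2 | 3.4 |
| 0.7 | 1.0 | 0.9 | 0.0483 | 41% | 14.5 | 6.0 |

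At a median of 0.6 the share runs from 13% to 54%, and the count from about 0 to 4 per 300. At a median of 0.7 with the widest spread, the upper ends reach 55% and about 6. The largest share and the largest count occur at different correlations.

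**The case against.** The strongest reply is that nobody disappears. A subject with ALT 9 and AST 4 is counted under ALT at 8 times ULN or more and under AST between 3 and 5. Having met a criterion, the subject goes into Listings 16.2.32 and 16.2.33, and is also in the plots of peak bilirubin against peak ALT and peak AST. The Hy's Law row asks for ALT or AST above 3 times ULN, so it does not use the joint rows. All of this stands. A reader might infer that severe liver cases drop out of the safety reporting, or that the Hy's Law screen is weakened; the documents do not support either inference.

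Second, the analysis is descriptive with one treatment group, and the liver criteria in Protocol Appendix 8 are built on ALT with bilirubin, INR, symptoms or persistence, never on ALT and AST jointly. The SAP does not name the joint rows as its measure of concurrent elevation, and it promises no total for both enzymes above 3 times ULN. This also stands, and it limits the importance of the point.

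Third, the SAP never says in words how a joint grade is assigned. A programmer might grade by the lower or the higher enzyme. An undercount is therefore the result of the literal reading, not a certainty about the final table. This does not remove the point: ALT 10 with AST 4 would land in the lowest row, in the highest row or in none, depending on the reading, and the text should settle which.

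**Conclusion.** The point holds, as a minor one. On the plain wording of Table 5, six of the nine band pairs with both enzymes above 3 times ULN fall in no joint row, and a worse subject can be left out while a milder one is counted. No other section supplies a rule that prevents this. The effect is limited to the three joint rows of Table 14.3.5.4, and no inferential result depends on them.

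The count of six in nine follows from the wording alone. The percentages and the counts per 300 do not: they rest wholly on the assumed log-normal model, with one sample per subject, and should not be read as estimates for this trial. They show only that the share can be appreciable while the number of subjects stays at a handful or fewer.

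**What to change.** Add a footnote to Table 5 defining the joint criterion by min(ALT/ULN, AST/ULN) in the same sample: >3 to <5, ≥5 to <8, ≥8. Each subject with both enzymes above 3 times ULN in one sample is then counted once, which fits the plan's rule of a single count at the worst grade. Pairs that already share a band keep their row, and the two-visit example moves from the lowest to the middle row.

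Cumulative rows (both >3, both ≥5, both ≥8) would also close the gap. They are not equivalent, because a subject with both enzymes at 8 or more is counted in all three, so they would have to be labelled as nested.

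The cost is one line of text and a small program change. The total joint count can only stay the same or rise. Grading by the lower multiple puts ALT 9 with AST 4 in the mildest joint row, so the severity of the higher enzyme has to be read from the single-enzyme rows.

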**Criteria 3**

**ALT  $\geq$ 3X ULN + Bilirubin  $\geq$ 2X ULN (>35% direct)**

or

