12.2.2 Serum Chemistry

Parameters include albumin, ALP, ALT, amylase, AST, blood urea nitrogen, calcium, calculated creatinine clearance, carbon dioxide, chloride, creatinine, creatinine kinase and subtypes, gamma-glutamyl transferase, globulin, glucose (non-fasting), high-density lipoprotein, lactate dehydrogenase, lipase, low-density lipoprotein, magnesium, phosphorus, potassium, sodium, total bilirubin, direct bilirubin, total cholesterol, total protein, triglycerides and uric acid. Visits include EOS Visit RB-US-13-0003 and Day 169 Week 25 (EOS INDV-6000-301)/ET visit.

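### The Hy's law row of SAP Table 5 requires ALP above ULN, so cases with ALP at or below ULN are not counted and the row can read zero when a case exists.

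*SAP*

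**What the plan says.** SAP section 12.2 plans a "Summary of potential hepatotoxicity for serum chemistry by type of criterion (shown in Table 5) and by analysis visit and at any time post baseline", in the Safety Analysis Set. The output is "Table 14.3.5.4 Summary of Potential Hepatotoxicity by Visit: Serum Chemistry - Safety Analysis Set".

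The last block of Table 5 is headed "HYs Law: (all must be met to meet Potential Hy's law". Its components are "ALT or AST > 3 x ULN", TBIL above 2xULN, and "ULN < Alkaline phosphatase (ALP) < 2xULN". The other rows band ALT alone, AST alone, ALT and AST jointly, and TBIL alone.

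The same section plans log/log plots of peak TBIL against peak AST and against peak ALT. For subjects who meet a criterion it also plans a listing of "their test results for ALT, AST, TBIL, ALP during study". On timing, SAP section 12.2.2 says "Visits include EOS Visit RB-US-13-0003 and Day 169 Week 25 (EOS INDV-6000-301)/ET visit", which gives one scheduled post-baseline panel. Unscheduled tests are possible and enter the any-time summary.

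Protocol Appendix 8, Criteria 3, has its own combined signal. The first of its two alternatives is ALT at or above 3xULN with bilirubin at or above "2X ULN (>35% direct"). It sets no ALP condition.

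**The concern.** Because all components must hold, the ALP condition is binding at both ends. The upper limit drops subjects with marked ALP elevation. The lower limit drops subjects with no ALP elevation. Only mild elevation remains, so inclusion is not monotone in ALP: a subject goes from not counted, to counted, and back to not counted as ALP rises. The SAP gives no reason for the lower limit.

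This is the only criterion in Table 5 that joins transaminases to bilirubin within a subject, and SAP section 12.1.7 makes hepatic disorders a topic of special interest. A reader will take the row carrying the Hy's law label at face value. With few cases expected, missing one or two can change the row from a signal to a zero.

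**Working it through.** **Inputs.** The rule and thresholds come from SAP Table 5. The planned size of about 300 comes from SAP section 18.0. The documents give no figure for the share *q* of true cases with ALP at or below ULN, so *q* is an assumption, shown at 0.1, 0.5 and 0.9. A true case here means ALT or AST >3xULN, TBIL >2xULN and ALP <2xULN, that is, the SAP's own rule without its lower limit. The plan states no figure to reproduce.

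**Step 1: the rule as written.** Take a test subject with ALT 10x, AST 8x and TBIL 4xULN, and vary ALP.

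| ALP (xULN) | As written (1 < ALP < 2) | Lower limit removed (ALP < 2) |
|---|---|---|
| 0.5, 0.8, 0.99, 1.0 | not counted | counted |
| 1.01, 1.5, 1.99 | counted | counted |
| 2.0, 2.5 | not counted | not counted |

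The two rules differ only at ALP at or below ULN. The ALT and bilirubin thresholds of protocol Appendix 8, Criteria 3, are met at every ALP value in the table (the direct-bilirubin condition is taken as met).

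**Step 2: is the limit relaxed elsewhere?** SAP section 20.9 adjusts laboratory classifications for LDH, total bilirubin, AST, HDL-C and GGT. It does not mention ALP, and no other section changes the criterion.

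**Step 3: chance that the row reads zero.** With *k* independent true cases, all are missed with probability *q*^*k*.

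| True cases *k* | *q* = 0.1 | *q* = 0.5 | *q* = 0.9 |
|---|---|---|---|
| 1 | 0.10 | 0.50 | 0.90 |
| 2 | 0.01 | 0.25 | 0.81 |
| 3 | 0.001 | 0.125 | 0.73 |

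**Step 4: what a zero would support.** If 0 of 300 are counted, the one-sided 95% upper bound on the rate of cases the row can see is 1 − 0.05^(1/300) = 0.994%. That rate equals the true-case rate times (1 − *q*), so the bound for all true cases is 0.994% / (1 − *q*):

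- *q* = 0.1: 0.994 / 0.9 = 1.10%
- *q* = 0.5: 0.994 / 0.5 = 1.99%
- *q* = 0.9: 0.994 / 0.1 = 9.94%

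**A smaller point in the same table.** The joint ALT and AST rows require both enzymes to fall in the same band. Read literally, a subject with ALT 9x and AST 6xULN fits neither the 5-to-8 row (ALT is too high) nor the 8-and-above row (AST is too low). Assigning subjects to the worst applicable grade does not help, because no joint grade above 3xULN applies. Each enzyme is still counted in its own row.

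**The case against.** The strongest reply is that little is lost. The missed subject still appears in the ALT or AST rows and the TBIL row, in Listings 16.2.32 and 16.2.33 and, for values in the Treatment Period, in Figures 14.3.5.4.1 and 14.3.5.4.2. If the abnormality is recorded as an adverse event, the hepatic TEAE summary may pick it up as well. The study is single-arm and descriptive, and on-study handling follows protocol Appendix 8, not Table 5. All of that stands. It limits the consequence to one row, but that row is still wrong. The separate rows do not link the enzyme and bilirubin elevations to one subject, so a reader would need the plots or listings to see that the count is short.

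A second reply is that Appendix 8 is weak evidence: it governs management, uses ALT only, adds a direct-bilirubin condition and does not use the Hy's law name. That is fair, and the contrast is only supporting. The conclusion rests on the logic of Table 5 itself. It is also true that the documents contain no independent definition that fixes the upper limit at 2xULN. The proposed change keeps the SAP's own upper limit and removes only the unexplained lower one.

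A third reply is that the probabilities are illustrative. They are: *q* has no source, the figures are conditional on one to three cases occurring, and the SAP plans no confidence bound. They show what a zero would mean and do not forecast how many cases there will be.

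**Conclusion.** The concern holds. Followed exactly, Table 5 leaves out every subject who meets the transaminase and bilirubin conditions with ALP at or below ULN, so the Hy's law row of Table 14.3.5.4 can be falsely zero. That conclusion needs no assumption. Its size does. Over an assumed *q* of 0.1 to 0.9, a single true case is missed with probability 0.10 to 0.90, and the upper bound implied by 0 of 300 moves from 0.99% to between 1.1% and 9.9%. The bound also assumes that all 300 subjects have evaluable post-baseline ALT or AST, TBIL and ALP. The error is confined to this row and the data remain visible elsewhere in the report. It should be fixed, but it does not threaten the study.

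**What to change.** In SAP Table 5, replace the third Hy's law condition with ALP < 2xULN, with no lower limit, and change the program for Table 14.3.5.4 to match. Optionally add a row for ALT or AST >3xULN with TBIL >2xULN regardless of ALP. That row would also show subjects with ALP at or above 2xULN, whom neither version of the rule counts. As a minor tidy-up, band the joint rows on the smaller of ALT and AST (both in xULN), so that ALT 9x with AST 6xULN falls in the 5-to-8 band.

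The cost is a one-line text edit and a small program change. ALP is already collected and listed, so no new data are needed, and clinical management is untouched. The Hy's law count can only stay the same or rise. If the joint rows are re-banded, a lower joint band may fall as subjects move to a higher one.
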